## **Human Subjects Protection**

### **Subject Recruitment Methods**

Potential candidates for the study will be identified based on the posting for the surgical procedure of elective primary anterior approach total hip arthroplasty. Patients will be approached during their preoperative assessment clinic visit for eligibility and told about the study in detail, including any known or possible risks, benefits, and alternatives. They will be advised there will be no financial incentive to participate. Potential subjects will also be recruited over the phone if they are not scheduled for a preoperative evaluation by anesthesia. They will be identified by the surgery schedule. Upon phone discussion they demonstrate interest a copy of the IRB approved informed consent form will be mailed to them to allow for adequate review of the study prior to the morning of surgery. . Written informed consent will be obtained and scanned into the EMR during that visit, if they consent, or on the day of surgery, if they need more time to deliberate on enrolling. Ample opportunity to ask questions will be given both during this preoperative visit and on day of surgery. All patients meeting the aforementioned eligibility criteria, regardless of gender, age, race, and ASA physical status, will be offered to participate.

### **Informed Consent**

Written informed consent will be obtained from each subject who agrees to enroll, scanned, and uploaded into the patient’s EMR for permanent storage. Each patient will have the opportunity at any time to decline enrollment, withdraw informed consent, and have their data removed from the dataset and destroyed at any point in time.

### **Confidentiality and Privacy**

Confidentiality will be protected by collecting only the requisite information required to assess the study outcomes, minimizing the collection of any information that could directly identify subjects. Each patient will be assigned a unique study identifier that will appear on the data collection form, and any protected health information that may directly identify the patient corresponding to the unique study identifier will be kept secure with access limited to designated study personnel. Following collection of all data, subject identifying information will be destroyed at the earliest opportunity, consistent with data validation and study design, producing an anonymous data set for analysis. All patient information collected will be kept confidential during recruitment as well as the remainder of the study. All identifying protected health information will be de-identified in the electronic database during data collection, which will be encrypted and secured in the Atrium Health Wake Forest Baptist private servers and only accessible by two-factor authenticated, password-protected computers. Only selected research personnel will have access to the dataset. No reference to any individual participant will appear in reports, presentations, or publications that may arise from the study.

### **Data and Safety Monitoring**

The principal investigators will be responsible for overall monitoring of the data and safety of study participants and will be assisted by other members of the research personnel in the identification of any safety concerns.

**Reporting of Unanticipated Problems, Adverse Events, or Deviations**

Each participating attending anesthesiologist will report to the principal investigators about any protocol violations, unanticipated problems with the protocol, or adverse events, which will promptly be reported to the IRB and corresponding government agency, if appropriate.

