### **Randomization**

Prior to beginning any regional anesthesia procedures, each patient will be randomized to one of the aforementioned treatment arms consisting of LPB or PENG block by research personnel and/or the attending anesthesiologist in charge of the patient's care. Randomization will occur in blocks of sequentially numbered opaque envelopes. Patients will be blinded to their treatment arm assignment, as will all research personnel who collect outcome data. Patient blinding will occur through the use of a sham block procedure as detailed below.

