### **Interventions**

Once randomization occurs, standard American Society of Anesthesiology (ASA) monitors and supplemental oxygen will be applied to the patient, and a timeout procedure will be conducted to verify all patient data and paperwork are correct. Unless the patient has a contraindication, each patient will also receive a weight-appropriate dose of acetaminophen and celecoxib, or meloxicam (if the patient has an allergy to sulfonamide medications or to celecoxib) at this time.

All blocks will be performed by an experienced faculty anesthesiologist well versed in the performance of LPB and PENG blocks, or by a regional anesthesia fellow directly supervised by a regional anesthesia specialized faculty anesthesiologist. Sedation for block placement will be administered using midazolam and fentanyl titrated to patient comfort, at the discretion of the attending anesthesiologist performing or supervising the regional anesthesia procedures. All subjects will start in the supine position, and their relevant anatomy for PENG block will be imaged using an ultrasound as described previously, after skin preparation with chlorhexidine solution. All subjects will then receive a skin wheal using 1mL of 1% lidocaine at the skin entry site for a typical PENG block. Those subjects assigned to the PENG treatment arm will subsequently receive a PENG block using 20mL of 0.2% ropivacaine with 1:400,000 epinephrine dosed in 5mL increments with negative aspiration beforehand and between each aliquot. All subjects will then be transitioned to lateral decubitus positioning with the surgical

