## Measurements

Following the completion of surgery, all subjects will be brought to the post-anesthesia care unit (PACU) for recovery, where they will recover until satisfactory resolution of spinal block as judged by an attending anesthesiologist is shown. Subjects will then be transported to an inpatient room, where nurses will monitor their vital signs and pain scores regularly. Subjects will receive standard of care pain medications for postoperative pain management as indicated. Subjects will continue to receive scheduled acetaminophen 1000mg every six hours (or 15mg/kg if their weight is below 65kg), and the NSAID administered preoperatively (either celecoxib 200mg twice daily or meloxicam 15mg once daily) barring any contraindication such as renal impairment or vascular disease. Oxycodone every four hours may also be administered as needed with dose ranges determined by the Davie Medical Center perioperative surgical home anesthesiologist consulted for postoperative care, or another narcotic at equipotent dosages if they have a contraindication to oxycodone. Alternatively, they may receive combination products such as Percocet (oxycodone/acetaminophen) or Vicodin/Norco (hydrocodone/acetaminophen) instead, with the acetaminophen dosage adjusted accordingly. All

opioids will be converted to oxycodone equivalents to allow for appropriate comparison using a widely available dose conversion table.

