Nurses will chart vital signs and medication administration in the electronic medical record (EMR) as per our standard protocol. Research personnel will measure patient-reported NRS pain scores at rest and with movement for each time by patient interaction, either face to face, or by calling the patient's room or phone numbers. This will include the primary outcome of patient-rated pain with movement of the surgical extremity on the NRS pain scale at six hours after block placement (roughly correlating to two hours after arrival to their room) as well as secondary outcomes that include but are not limited to pain at rest and with movement at 12, 18, and 24 hours following block placement, and strength to straight leg raise at six hours post-block placement. The cumulative 24 hour opioid consumption will be abstracted from the EMR for doses received while admitted, and documented by the patient in their pain journal and abstracted via phone call after their discharge, if this occurs prior to 24 hours after the block. Physical therapists will also document their encounters in the EMR, including but not limited to the secondary outcome of distance ambulated during their first session in feet. These metrics will be accessed, abstracted, de-identified, and analyzed by research personnel who are blinded to group allocation.

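### Adverse events have only unblinded named reporters and no structured question at the blinded 6 to 24 hour contacts, so later harms may be under-recorded and recording may differ by arm

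*Combined protocol and SAP*

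**What the plan says.** The section on reporting of unanticipated problems, adverse events and deviations names one source of reports: "Each participating attending anesthesiologist will report to the principal investigators about any protocol violations, unanticipated problems with the protocol, or adverse events". It gives no event list, definition, collection window or form.

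Under Interventions, "All blocks will be performed by an experienced faculty anesthesiologist well versed in the performance of LPB and PENG blocks", or by a fellow whom a faculty anesthesiologist supervises directly. Under Randomization, the patient is assigned "by research personnel and/or the attending anesthesiologist in charge of the patient's care". The same section sets out the blinding: "Patients will be blinded to their treatment arm assignment, as will all research personnel who collect outcome data". Attending anesthesiologists are not on that list.

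Data and Safety Monitoring adds that the principal investigators "will be assisted by other members of the research personnel in the identification of any safety concerns". It attaches no question, form or time point to this role.

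Under Measurements, "Research personnel will measure patient-reported NRS pain scores at rest and with movement for each time by patient interaction", face to face or by phone. The items named are pain, straight-leg-raise strength at 6 hours and opioid use, with walking distance taken from the physical therapy entries. The wording leaves the list open to further items. No adverse event item is named. Safety is not an outcome under Objectives, and Data Analysis plans no comparison of adverse events.

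**The concern.** The Summary/Purpose/Rationale section justifies the trial partly by leg weakness: the lumbar plexus block causes it, and the PENG block does not do so consistently. A fall or the leg giving way is a foreseeable result of weakness, and could happen when the patient is mobilized on the ward or at home. In that period the scheduled study contacts are made by blinded staff, for whom no safety question is written.

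The only named reporters know which block was given, and the protocol itself leads them to expect weakness with one of the two. Spontaneous reporting by people with that knowledge can miss events in both arms. It can also record them more readily in one arm, so it could create or hide a difference. If equivalent analgesia is shown and practice changes, readers will want to know whether harms differed, and the safety record may not be able to tell them.

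**Working it through.** **The plan's own figure.** The only calculated figure in the plan is the sample size. With SD 2.0, margin 1, one-sided alpha 0.05, power 80% and a true difference of zero, n = 2 × [2.0 × (1.645 + 1.282) / 1]² = 68.5, so 69 per arm. This agrees with Power Analysis. It concerns pain only, and nothing below changes it.

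**Who sees the patient, and who knows the arm**
- Block placement: the attending performs or supervises, and so knows the arm. This person is a named adverse event reporter.
- PACU: patients stay "where they will recover until satisfactory resolution of spinal block as judged by an attending anesthesiologist is shown". This need not be the attending who placed the block.
- Ward: oxycodone is given "with dose ranges determined by the Davie Medical Center perioperative surgical home anesthesiologist consulted for postoperative care". The protocol does not say whether this person counts as a participating attending, knows the arm or asks about harms. Nurses monitor vital signs and pain scores.
- 6, 12 and 24 hours, on the ward or by phone: blinded research personnel. The 18 hour score may be taken in retrospect at 24 hours. No adverse event question is described.

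**Share of follow-up after PACU.** Measurements places the 6 hour score roughly two hours after arrival in the room. Arrival is therefore at about 6 − 2 = 4 hours, and (24 − 4)/24 = 83% of follow-up comes later. This is a share of clock time, not of events.

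**What an empty record would show.** With 80 per arm and no recorded events, the one-sided 95% upper bound on the recorded event rate is 1 − 0.05^(1/80) = 3.675%. It bounds the true rate only if capture is complete. At an assumed 50% capture, the bound on the true rate is 3.675% / 0.5 = 7.35%.

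**Unequal capture (all rates assumed).** Take a true risk of 10% in both arms, so 80 × 0.10 = 8 events each.
- Capture of 100% and 50%: 8 versus 8 × 0.5 = 4 recorded events.
- Capture of 80% and 50%: recorded rates of 8% versus 5%.

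Both differences are false.

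**Equal but incomplete capture (all rates assumed).** Take true risks of 20% and 5%, 80 per arm and a two-sided 5% test of two proportions.
- Full capture: pooled SE = √(2 × 0.125 × 0.875/80) = 0.0523 and unpooled SE = √((0.16 + 0.0475)/80) = 0.0509. Then (0.15 − 1.96 × 0.0523)/0.0509 = 0.93, and power is about 82%.
- Capture of 75%: power about 69%.
- Capture of 50%: power about 50%.
- Capture of 25%: power about 27%.

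**The case against.** The case against is substantial, and several parts of it stand.

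- A reader might infer that research staff have no safety role. Data and Safety Monitoring gives them a general one. What is missing is a procedure.
- A reader might infer that Measurements restricts what the blinded staff collect. Its list is open. It permits safety items but specifies none.
- A reader might infer that anesthesiologist contact ends in PACU. The reporting section sets no time limit, and an anesthesiologist is consulted for postoperative care on the ward. Nurses also monitor patients there, though no route from their notes to the principal investigators is described.
- A reader might conclude that later harms are missed and that the arms cannot be compared fairly. The documents support only a risk of both. Capture rates are unknown, and no between-arm safety comparison is planned that could be biased.
- Weakness itself is partly covered, by blinded strength testing at 6 hours and by walking distance at the first therapy session. Neither records a harm that follows from weakness.
- Confidentiality and Privacy mentions a data collection form that is not reproduced, and the consent pages were not available for this review. An adverse event field may exist there. The protocol text would still need to say when it is used and by whom.

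There is also a fair objection to the remedy. Asking about numbness or the block site at 6 or 12 hours would record expected block effects as events, and could reveal the arm to the person scoring pain. The timing of the questions has to deal with this.

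**Conclusion.** The gap is real but limited. The only named adverse event reporters know the allocation, the blinded staff have a general safety role without a procedure, and no structured question is described at the 6 to 24 hour contacts. Later harms may be under-recorded, and recording may differ by arm. The direction of any bias cannot be predicted.

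The equivalence test of movement pain at 6 hours is unaffected. What is weakened is any statement about relative safety made afterwards. The size cannot be estimated, because the documents give no event or capture rates. The figures above show only how sensitive such a statement would be under assumed rates. The conclusion also assumes that the data collection form, which was not seen, contains no structured adverse event items. The change is worth making because it is cheap and because answers not sought within the 24 hours are hard to recover later.

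**What to change.** **Measurements and the reporting section.** Have the blinded research personnel ask the same short fixed questions at the existing contacts, always after pain and strength have been scored:
- at 6, 12 and 24 hours: any fall or giving way of the leg, and any unplanned medical contact;
- at 24 hours only, once all pain scores, including the retrospective 18 hour score, are recorded: persisting numbness or weakness, and any block-site problem.

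This order keeps the primary endpoint clear of the questions and holds the most revealing ones until scoring is finished. Add the same items to the pain journal, at the same time points. Positive answers go to the principal investigators alongside the attendings' reports.

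**EMR abstraction.** From the physical therapy entries already being read, also abstract falls and sessions stopped for weakness.

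**Data Analysis.** Add a descriptive table of events by randomized arm with confidence intervals, without a hypothesis test.

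**Cost.** About a minute per contact, a few form and journal fields, one table, more events to review, and some recording of expected block effects. No new visits or patients are needed, and the sample size is unchanged.
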